#### 8.4.2.1. Prospective Data Collection

When the treating physician has an indication to start the studied medication, the eligibility of the patient will be assessed (IBD diagnosis and >16 years of age). When an eligible patient is identified, a patient information form will be distributed, and IC obtained. The treating physician or IBD nurse from the participating center fills out patient characteristics (gender, year of birth, disease information) in the new patient eCRF (software.memic.unimaas.nl) and a code is created which will be used from here on after.

#### 8.4.2.2. Retrospective Data Collection

Patients who started in standard care with the studied medication and finished follow-up will retrospectively and anonymously be registered in the ICC registry. Therefore, we will not ask for a patient's IC.

#### 8.4.2.3. Pseudonymization

Each participant is assigned a unique code, consisting of a number for each center (e.g. 01 for Maastricht University Medical Center) and a 5-digit sequence number (00001 etc.): 01.00001. This code will be used for all study-related documents and materials. The participant's identity cannot be traced directly via this code. Only the local principal investigator and local coordinating researcher will have access to the local source file, in which the unique code is linked to the personal data such as name and date of birth. This file will be kept in a secure site on the hospital/institutions network and access to this file will be restricted to the clinicians participating in the study at this local center.

#### 8.4.2.4. Standardized Treatment Protocol

The following follow-up protocol is based on current standard of care. On the day of initiating therapy, the Week 0 visit will be filled out. The next visits reflect the minimum acquired visits in routine care and are scheduled on Week 12, Week 24, Week 52, and once yearly up to 10 years after initiation of treatment. If a patient or physician decides to discontinue the medication, the medication discontinuation form will be filled out and further registration is discontinued. All patients receive standard care and no additional questions, blood samples, interventions, questionnaires, or other activities have to be performed.

If a patient discontinues the medication and initiates another treatment that is included in the ICC Registry, the follow-up is again at Week 12, 24, 52, and 1 visit yearly.

#### 8.4.2.4.1. Week 0 (Baseline)

Clinical data on demographics, date of diagnosis, IBD phenotype and phenotype history, location of previous IBD surgery, medical history, IBD medication history, and smoking status will be collected. Furthermore, the current clinical disease activity (Harvey-Bradshaw Index [HBI]/Simple Clinical Colitis Activity Index [SCCAI]), biochemical data (Hb, thrombocytes,

leucocytes, alanine aminotransferase [ALT], alkaline phosphatase, C-reactive protein [CRP], creatinine, fecal calprotectin), current IBD medication, and, if applicable, radiologic, and endoscopic information will be collected.

#### 8.4.2.4.2. Follow-up Visits (Week 12, 24, 52, Year 2, 3, 4, 5, 6, 7, 8, 9, 10)

During follow-up visits, the following information is collected: current clinical disease activity (HBI/SCCAI), biochemical data (Hb, thrombocytes, leucocytes, ALT, alkaline phosphatase, CRP, creatinine, fecal calprotectin), current IBD medication, complications (surgery, hospitalization), AEs (events related to medication and infections), and, if applicable, radiologic and endoscopic information.

Details of variables to be collected in ICC can be found in Annex 3 – Table 5.

#### 8.4.3. SWIBREG (SWE)

Baseline and follow-up data, including patient demographics, disease characteristics, and treatment will be based on data from SWIBREG and the Swedish Patient and Prescribed Drug Registers. SWIBREG data will be augmented with linkages to the Swedish Cancer, Contagious Diseases, Medical Birth, Causes of Death, and Total Population Registers.

Details of variables to be collected in SWIBREG can be found in Annex 3 – Table 5.

#### 8.4.3.1. SWIBREG (Main Data Source)

The Swedish Quality Register for patients with IBD (SWIBREG), including UC, is a structured collection of personal data that was initiated to systematically and continuously develop and safeguard quality of IBD care in Sweden (Ludvigsson et al., 2019). In SWIBREG, individuallevel data have been collected from most Swedish IBD caregivers since 2005. The positive predictive value for a UC diagnosis in SWIBREG is very high (96% [95% confidence interval [CI]: 89-99]) (Jakobsson et al., 2017).

SWIBREG includes data on conventional therapies, biological treatment, surgeries, smoking, disease activity, patient-reported outcome measures, and patient-experienced measures. Although SWIBREG does not have a national coverage similar to National Patient Register (NPR) or Prescribed Drug Register (PDR), the 2 common sources of data for identifying patients with IBD in Sweden, its data allows for analysis of safety of IBD treatments over a relatively long follow-up period. Although safety events are not routinely collected in SWIBREG, data linkage to other nationwide healthcare registers (NPR, cancer register, cause of death register, contagious disease register, medical birth register, and the total population register) enables capturing all censoring events and safety endpoints of interest. Additionally, the PDR allows for confirmation of dispensed prescriptions (Bröms et al., 2021). In addition to data on safety outcomes and baseline comorbidities or disease history, SWIBREG is also the source of patients with UC naive to advanced therapies/immunomodulators/immunosuppressants agents.

#### 8.4.3.2. National Patient Register and Prescribed Drug Register

The NPR provides information on all hospitalized (inpatient treated) patients (Ludvigsson et al., 2011), and all visits to nonprimary outpatient care (such as a visit to a gastroenterologist). Diagnoses are assigned by the physician, as well as date of discharge and discharging hospital for inpatient care, and hospital department. Diagnoses are coded according to the International Classification of Diseases (ICD), with version 8 used until 1986, version 9 from 1987 to 1996, and ICD10 since 1997. Due to routine validation and acquisition processes, data on hospital visits become available for research the earliest during the next calendar year. The PDR provides all filled prescriptions in Sweden from 1 July 2005, and may be used to aid correct classification of patients by their history of retrieved IBD therapies, or to define subcohorts based on treatment switches (Wettermark et al., 2007). A recent validation study has indicated that the coverage of the infusion drugs in the PDR is not optimal (Bröms et al., 2021).

#### 8.4.3.3. The Contagious Disease Register

The Swedish Contagious Disease Register (SmiNet), established in 1971, provides events reported according to the Communicable Diseases Act and the Communicable Diseases Ordinance on diseases that have mandatory reporting in Sweden (e.g. TB).

#### 8.4.3.4. The Swedish Cancer Register

The Swedish Cancer Register was established in 1958 and provides data on date of cancer (and some selected precancers) onset, and type of cancer according to the ICD classification and morphology/histology (Barlow et al., 2009). About 99% of cancers have been morphologically verified. Reporting of incident cancers (including invasive malignancies as well as cancer in situ) is mandatory and semi-automated, resulting in an estimated coverage greater than 95%.

## 8.4.3.5. The Medical Birth Register

The Medical Birth Register contains prospectively provided data from antenatal, obstetric, and neonatal records since 1973, and covers all live and still births (but not all miscarriages) in Sweden. Among the variables collected are maternal age, parity, smoking and family situation in early pregnancy, and the infant's birth weight and length, gestational age (primarily based on ultrasound dating), and Apgar score. Complications and mother's and infant's morbidities are coded according to the ICD, with version 8 used until 1986, version 9 from 1987 to 1996, and ICD10 since 1997 onwards (Cnattingius et al., 1990).

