The safety information in the HCP Guide provides context and risk management advice for key safety aspects of the SmPC, namely (key safety aspects with updates in the HCP Guide after Article 20 are listed in *italics*):

- Serious and opportunistic infections
- Herpes zoster
- Potential risk of birth defects if filgotinib is taken during pregnancy

- Potential risk of VTE
- Potential risk of MACE
- Potential risk of malignancy
- Prescribing in elderly patients and in patients with risk factors for VTE, MACE, and malignancy

The SmPC specifies that the recommended dose for induction treatment in UC is 200 mg once daily. The recommended dose for maintenance treatment is 200 mg once daily. In patients aged 65 years or older or at higher risk of VTE, MACE and malignancy, the recommended dose is 200 mg once daily for the induction treatment which may be prolonged up to Week 22, and 100 mg once daily for maintenance treatment. In case of flare of the disease, the dose may be escalated to 200 mg once daily. For long term treatment, the lowest effective dose should be used (as per SmPC Section 4.2 'Posology and method of administration').

In patients with active tuberculosis (TB), active serious infections, or in women who are pregnant treatment with filgotinib is contraindicated (as per SmPC Section 4.3 'Contraindications').

Additional aspects as per updated SmPC Section 4.4 'Special warnings and precautions for use' are listed below:

*Use in patients 65 years of age and older*: Considering the increased risk of MACE, malignancies, serious infections, and all-cause mortality in patients 65 years of age and older, filgotinib should only be used in these patients if no suitable treatment alternatives are available.

*Infections*: As there is a higher incidence of infections in the elderly and in the diabetic populations in general, caution should be used when treating the elderly and patients with diabetes.

*Malignancy*: In patients 65 years of age and older, patients who are current or past long-time smokers, or with other malignancy risk factors (e.g. current malignancy or history of malignancy), filgotinib should only be used if no suitable treatment alternatives are available.

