#### Follow-up

Among women starting filgotinib, the number and proportion who become pregnant during follow-up will be reported. Similarly, the number and proportion of patients who have a new

diagnosis of TB during follow-up, a serious acute infection, a diagnosis of viral hepatitis, concomitant treatment with other immunosuppressants, or who are administered a live attenuated vaccine will be reported. In patients with TB, or a serious infection identified during follow-up, it will be assessed whether treatment was stopped or interrupted after the diagnosis. The proportion of patients who have a test for lipids at around 12 weeks since initiation of filgotinib will be reported.

Should a VTE event occur, subsequent changes to filgotinib use will be reported (filgotinib treatment persistence or discontinuation).

Assessment of the filgotinib maintenance dose during follow-up will also be done in the subgroup of patients at high risk of MACE, VTE, or malignancy. In addition, the average daily dose during the maintenance period and the duration of use during the follow-up period will be reported.

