Immunomodulators /- suppressants (e.g. tacrolimus, azathioprine, mercaptopurine)	yes	yes	yes	
Other (aminosalicylates, corticosteroids)	yes (not always available; might be in medical report)	yes	yes	
Reasons for switching	yes	yes	yes (SWIBREG, good coverage for targeted therapies)	
Intolerance/adverse events	yes	yes	yes	
Lack of efficacy	yes	yes	yes	
Other	yes	yes	yes	
SmPC section 4.1: Indication				
Severity of UC (moderate to severe)	yes (some data in ENEIDA may be available or alternatively through chart abstraction [through proxies such as drug switching, addition of drugs, colectomy etc.])	yes (SCCAI, CRP, fecal calprotectin and if available radiologic and endoscopic information)	yes (Severity of UC based on proxies such as exposure to immunomodulators or different lines of targeted therapies (= moderate to severe UC) or proxies for flares (e.g., steroid prescriptions, steps in the treatment ladder, hospitalizations with UC as main diagnosis, UC-related surgery, extent/location of	

Variable	Availability in individual registries yes/no (additional comments)			
	ENEIDA (ES)	ICC (NL)	SWIBREG (SE)	
			disease in UC, history of prior biologic use, disease duration and UC-related treatment exposure)	
Date of severity assessment	yes (if defined by medical therapies)	yes	yes	
Date of filgotinib initiation (to ascertain new users) = index date	yes	yes	yes	
Age at index date	yes	yes	yes	
SmPC section 4.2: Posology (Induction treatment)				
Initial filgotinib dose (induction treatment)	yes (if not available, might be in medical report)	yes	yes	
SmPC section 4.3: Contraindications				
Active TB at index date	yes (if not available, might be in medical report)	yes	yes (SmiNet, Population Register)	
Dx date TB	yes (if not available, might be in medical report)	yes	yes (SmiNet, Population Register)	
Active serious infection (SI) at index date	yes (if not available, might be in medical report)	yes	yes (Population Register, PDR)	
Dx date SI	yes (if not available, might be in medical report)	yes	yes (Population Register, PDR)	
Current pregnancy at index date	yes (if not available, might be in medical report)	yes	yes (Medical Birth Register)	

Variable	Availability in individual registries yes/no (additional comments)				
	ENEIDA (ES)	ICC (NL)	SWIBREG (SE)		
Date of pregnancy	yes	yes	yes (Medical Birth Register)		
SmPC section 4.4: Special warnings and precautions for use (Box warning)					
(Age 65+)	yes	yes	yes		

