Variable	Availability in individual registries yes/no (additional comments)		
	ENEIDA (ES)	ICC (NL)	SWIBREG (SE)
			hospitalizations with IBD as the main diagnostic listing will be treated as flares)
Date of hospitalization	no (might be in medical report)	yes	yes (NPR)
Hx of blood clotting disorder or blood clots	no (might be in medical report)	yes (as part of medical history/comorbidity)	yes (NPR)
Concomitant use of combined hormonal contraceptives	no (might be in medical report)	no (but can be added)	yes (NPR)
Concomitant use of hormone replacement therapy	no (might be in medical report)	no (but can be added)	yes (NPR)
SmPC section 4.6: Fertility, pregnancy and lactation			
Advice on contraception in women of childbearing potential	no	no	no
Breastfeeding	no (might be in medical report)	no (but can be added)	no
	Variables assessed during follo	w-up	
Filgotininb treatment status			
Discontinuation	yes	yes	yes (SWIBREG, PDR)
Date of discontinuation	yes	yes	yes (SWIBREG, PDR)
SmPC section 4.2: Posology (Maintenance treatment)			
Maintenance filgotinib dose (after a maximum of 22 weeks of induction treatment)	yes (if not available, might be in medical report)	yes	yes (PDR)
SmPC section 4.3: Contraindications			

Variable	Availabil (ad		ries
	ENEIDA (ES)	ICC (NL)	SWIBREG (SE)
Tuberculosis (TB)	yes (if not available, might be in medical report)	yes	yes (SmiNet)
Dx date TB	yes (if not available, might be in medical report)	yes	yes (SmiNet)
Serious infection (SI)	yes (if not available, might be in medical report; a proxy definition of infection severity can be used to align with the definition of the other registries, based on information available from an eCRF field on the outcome of the infection [such as death, hospital admission])	yes (infections that lead to hospitalization or intravenously administrated antibiotic or antiviral medication)	yes (ICD-10 codes as recorded in the NPR or the 'infectious disease register' [for tuberculosis] including overall codes for e.g. sepsis or septic shock or for specific infectious disease categories being the main or contributory diagnostic listing for a hospitalization)
Dx date SI	yes (if not available, might be in medical report)	yes	yes (NPR)
Pregnancy	yes (if not available, might be in medical report)	yes	yes (Medical Birth Register; could be retrieved following child birth)
Date of pregnancy	yes	yes	yes (Medical Birth Register; could be retrieved following child birth)

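### Swedish pregnancies come only from a birth register, so those that end early or are still ongoing at data cut-off are incompletely captured and the Swedish pregnancy figures are biased downward

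*Protocol*

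**What the plan says.** Section 6 of the protocol lists three contraindications: active tuberculosis, active serious infection and pregnancy. On the last it says that "in women who are pregnant treatment with filgotinib is contraindicated". Section 7 makes contraindicated use part of the adherence objective. Section 8.7 (Follow-up) adds a separate result: "Among women starting filgotinib, the number and proportion who become pregnant during follow-up will be reported".

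For Sweden, Annex 3, Table 5 gives a single source. Pregnancy at the index date is marked "yes (Medical Birth Register" with no second register named. Pregnancy during follow-up is marked "yes (Medical Birth Register; could be retrieved following child birth". Section 8.4.3.5 describes that register: it "covers all live and still births (but not all miscarriages) in Sweden". Terminations and ectopic pregnancies are not mentioned.

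Section 8.4.3.1 says of the Swedish linkage as a whole that it "enables capturing all censoring events and safety endpoints of interest". Section 8.9 does not list incomplete capture of pregnancy among the limitations. It names SWIBREG as the registry in which most variables will be available.

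**The concern.** The quantity promised is women who are, or become, pregnant while on filgotinib. The quantity the Swedish source delivers is closer to women with a pregnancy that reached a registered birth. Whether a Swedish pregnancy is counted thus depends in part on how it ended and on whether it had ended when the data were drawn.

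For adherence to a contraindication the outcome of the pregnancy is irrelevant: exposure during pregnancy is the event. Incomplete capture can only remove events from the count, so it makes adherence look better than it is. Few such events are to be expected in a cohort of at most 500 patients per registry, and losing one or two could decide whether the report says none or some. Table 5 gives a plain yes for this variable, although it flags other weak Swedish variables (smoking, BMI, blood counts) as poorly covered. A reader of the report would therefore have no reason to doubt the Swedish figure.

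**Working it through.** No figure in the protocol describes pregnancy ascertainment, so the check is mainly a comparison of passages.

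**Step 1: what the named source holds, by outcome of the pregnancy**

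- Live birth or stillbirth on record at data cut-off: captured (Section 8.4.3.5).
- Miscarriage: captured in part. The protocol says not all are covered, so some may be.
- Termination or ectopic pregnancy: not mentioned. Loss is inferred from coverage defined by births and from retrieval after childbirth.
- Ongoing at data cut-off: not retrievable until the birth.

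**Step 2: how far the cut-off matters**

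The observational period is 4 years from 10 March 2023, so it ends in March 2027. The footnote to the milestones says that linked data for a calendar year arrive about 13 months after year-end. Data for 2027 would then arrive around January 2029, which fits the stated end of data collection in Q1 2029. For the interim report, 2 years end in March 2025, and data for 2025 would arrive around January 2027, which fits Q1 2027. If births up to the end of that calendar year are used, most pregnancies ongoing at the end of observation could be found. The protocol does not say that births after the end of observation will be used. Section 8.6.3 says only that data are ordered at the end of follow-up or at the interim cut-off. This part of the loss therefore depends on the extract. The loss of pregnancies that end early does not.

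**Step 3: whether another source is at hand**

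Section 8.4.3.2 says: "The NPR provides information on all hospitalized (inpatient treated) patients", and adds "all visits to nonprimary outpatient care (such as a visit to a gastroenterologist". Its diagnoses have been coded in ICD-10 since 1997. Section 8.6.3 links the study population to all the health registers. Table 5 already uses the National Patient Register for cardiovascular history, VTE, viral hepatitis, herpes zoster and other variables, but not for pregnancy.

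**Step 4: direction and size**

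Let f be the share of pregnancies on treatment that the Medical Birth Register extract does not hold. Then

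observed proportion = true proportion × (1 − f), with 0 ≤ f ≤ 1.

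The only related figure in the plan is Table 3 in Section 8.5, the rule of 3 for detecting a contraindication. It reproduces: 3/0.01 = 300 and 3/0.02 = 150. The chance of at least one case at a true 1% and n = 300 is 1 − 0.99^300 = 95.1%. With incomplete capture, the size needed at a true 1% becomes 300/(1 − f), and the detection chance at n = 300 falls to 1 − (1 − 0.01 × (1 − f))^300. Both move the wrong way for any f above zero. No value of f, and nothing from which to derive one, stands in the protocol, so the sign is established and the size is not. Table 3 is illustrative and not specific to pregnancy. It is not itself in error.

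**The case against.** The strongest reply has four parts.

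- **The limit is disclosed.** Section 8.4.3.5 states the gap for miscarriages, Table 5 says that retrieval follows childbirth, and Section 8.9 says in general terms that registries differ in what they capture. This is true. But the disclosure sits in a register description, it does not change the stated source, and Section 8.9 draws no consequence for the pregnancy result.
- **Table 5 shows availability, and code lists belong in the SAP.** This stands in part: the code list itself can go there. But Table 5 fixes the source, and the ENCePP checklist in Annex 2 (item 6.2) points to Table 5 for how outcomes are defined and measured.
- **The gain from the National Patient Register is unproven.** This stands. The register does not cover primary care, and the protocol does not say how many early losses it would hold. Adding it can narrow the gap but not be shown to close it.
- **The effect is narrow.** This stands too: one contraindication of three, in one registry of three, among women only.

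A reader might also infer more than the documents support:

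- *All early losses are missed.* The wording is that not all miscarriages are covered, and the register also draws on antenatal records. Incompletely captured is as far as the text goes.
- *The share missed equals the share of pregnancies that end before birth.* The protocol gives no such share, and the step assumes that no early loss is ever captured.
- *Early losses are commoner among women exposed to filgotinib.* Nothing in the protocol bears on this.
- *ENEIDA and ICC capture pregnancy better.* This is not shown. For ENEIDA, Table 5 falls back on the medical report, chart abstraction needs new consent and is not done for the interim report, and Section 8.7.1.1 mostly reads missing information as absence. For ICC, Table 5 says yes, but pregnancy is not among the items listed for the baseline or follow-up visits in Section 8.4.2.4.

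**Conclusion.** The point holds in a limited form. If the plan is followed exactly as written, Swedish pregnancies on filgotinib that end early or have no birth on record at data cut-off are incompletely captured. Two Swedish results are biased downward: use of filgotinib in women pregnant at the index date, and the proportion who become pregnant during follow-up. These are separate measures, but both rest on the same register.

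The size cannot be computed from the documents. The direction rests on the stated coverage for miscarriages. For terminations and ectopic pregnancies it rests on an inference from birth-based coverage. For ongoing pregnancies it rests on how far beyond the end of observation the birth records run, which the protocol does not state. It would be wrong to read this as an understatement of contraindicated use as a whole, because tuberculosis and serious infection come from other sources.

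The change is worth making because the linked data to reduce the bias are already in the study.

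**What to change.** - **Table 5, both Swedish pregnancy entries:** define pregnancy as a Medical Birth Register record or a National Patient Register record with an ICD-10 pregnancy-related code, including miscarriage, termination and ectopic pregnancy.
- **Reporting:** give Swedish counts by source (birth register only, patient register only, both), so that the contribution of the second source can be seen.
- **Cut-off:** state the date to which birth records are extracted, and whether births after the end of observation are used to identify pregnancies that began on treatment.
- **Section 8.9:** state that losses managed outside inpatient or specialist outpatient care remain uncaptured, and that the remaining bias is toward undercounting.

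The cost is small: a code list applied to registers that are already linked, with no new data collection. The drawback is dating. The Medical Birth Register carries gestational age, whereas the start of a pregnancy found only in the National Patient Register will be approximate, so some of these pregnancies cannot be placed with certainty before or after the index date. They should be shown as such.
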